# 3.1. Discussion of Design

The study design has been well established. The design is based on previous BPH dutasteride monotherapy trials and the co-administration BPH trials. The trial includes a 4 week placebo run-in period to reduce subjective "placebo responses" in subsequent results reported after randomization with active treatment.

There is no placebo control group in this trial, since the clinical benefits from active treatments used in this trial have been previously demonstrated. Dutasteride 0.5mg and tamsulosin 0.2mg are both approved for treatment of BPH treatments either as monotherapies or in mutual co- administration.

The dose of tamsulosin 0.2mg is the approved and widely used dose in the Asia Pacific region. Tamsulosin PK data showed that in Japanese subjects taking tamsulosin 0.4mg, the Cmax was higher compared to Caucasian subjects taking the same dose. The lower dose of tamsulosin is preferred in Asia, considering a key complication associated with the higher dose; postural hypotension.

The pharmacokinetics of dutasteride and tamsulosin in Western subjects is well-understood (CIB). In contrast, pharmacokinetic data for these two drugs in Chinese subjects are limited. Following a request to provide this information from the Regulatory Authority in China, subjects of Chinese origin living in China will participate in a PPK sub-study in this study, which aims to characterize the PK of dutasteride when dosed in combination with tamsulosin to Chinese men with BPH.

The benefits of tamsulosin 0.2mg co-administered with dutasteride 0.5mg has been previously demonstrated in a Japanese phase III study where subjects were allowed to take tamsulosin 0.2mg concomitantly with dutasteride.

## 4. SUBJECT SELECTION AND DISCONTINUATION/ COMPLETION CRITERIA

# 4.1. Subject Selection Criteria

Deviations from inclusion and exclusion criteria are not allowed because they can potentially jeopardize the scientific integrity of the study, regulatory acceptability, or subject safety or rights. Therefore, adherence to the criteria as specified in the protocol is essential.

### 4.1.1. Number of Subjects

Approximately 586 men with symptomatic BPH will be randomized into the treatment phase. It is expected that approximately 1000 patients will need to be screened to allow

for a screening failure rate of approximately 40%. The overall enrolment target number may be adjusted depending on the actual experience of enrolment and retention of participants, to ensure that the overall evaluable subject number target is met. See Section 9.2.1 for sample size assumptions.

#### 4.1.2. Inclusion Criteria

Subjects eligible for enrolment in the study must meet all of the following criteria:

- 1. males, aged  $\geq$ 50 years
- 2. clinical diagnosis of BPH by medical history and physical examination, including a digital rectal examination (DRE)
- 3. International Prostate Symptom Score (IPSS) ≥12 points at Screening
- 4. prostate volume ≥30cc (by transrectal ultrasonography; TRUS)
- 5. total serum Prostate Specific Antigen (PSA) ≥1.5ng/mL and ≤ 10 ng/mL at Screening
- 6. maximum urinary flow rate (Qmax) >5mL/sec and ≤15mL/sec and minimum voided volume of≥125mL at Screening
- 7. Asparate aminotransferase (AST) and Alanine aminotransferase (ALT) < 2x upper limit of normal (ULN); alkaline phosphatase and bilirubin ≤ 1.5xULN (isolated bilirubin > 1.5xULN is acceptable if bilirubin is fractionated and direct bilirubin <35%)
- 8. Fluent and literate in local language with the ability to comprehend and record information on the IPSS, BHS, BII, and PAS- SFI questionnaires
- 9. Men with a female partner of childbearing potential must agree to use a condom up to 6 months after the last dose (applies only to countries where the local product monograph for dutasteride mandates condom use for men with a female partner of childbearing potential)

#### 4.1.3. Exclusion Criteria

Subjects meeting the following criteria must not be enrolled in the study:

*Medical Condition Exclusions:* 

1. History or evidence of prostate cancer (e.g. positive biopsy or ultrasound, suspicious DRE). Patients with suspicious ultrasound or DRE who have had a negative biopsy within the preceding 6 months and stable PSA are eligible for the study.

Note: If total serum PSA is >4ng/mL and unless PSA value has been stable for at least the past 2 years, the investigator should make every appropriate effort to exclude the possibility of prostate cancer, including consideration of prostate biopsy.

- 2. Previous prostatic surgery (including TURP, laser, HIFU (transrectal high intensity focused ultrasounds), thermotherapy, TUNA, (transurethral needle ablation), balloon dilatation, and stent replacement) or other invasive procedures to treat BPH.
- 3. History of flexible/rigid cystoscopy or other instrumentation of the urethra within 7 days prior to the Screening Visit. Catheterisation (<10F) is acceptable with no time restriction.
- 4. History of AUR within 3 months prior to Screening Visit.
- 5. Post-void residual volume >250mL (suprapubic ultrasound) at Screening.
- 6. Any conditions other than BPH, which may in the judgment of the investigator, result in urinary symptoms or changes in flow rate (e.g. neurogenic bladder, bladder neck contracture, urethral stricture, bladder malignancy, acute or chronic prostatitis, or acute or chronic urinary tract infections).
- 7. Unstable liver disease (chronic stable hepatitis B and C are acceptable if subject meets entry criteria).
- 8. History of renal insufficiency, or serum creatinine >1.5 times the upper limit of normal at Screening.
- 9. Any unstable, serious co-existing medical condition(s) including, but not limited to:
- a. Myocardial infarction, coronary bypass surgery, unstable angina, cardiac arrhythmias, clinically evident congestive heart failure, or cerebrovascular accident within 6 months prior to Screening visit; uncontrolled diabetes or peptic ulcer disease which is uncontrolled by medical management.
- b. Postural hypotension, dizziness, vertigo or any other signs and symptoms of orthostasis, which in the opinion of the investigator could be exacerbated by tamsulosin and result in putting the subject at risk of injury.
- c. Any serious and/or unstable pre-existing medical, psychiatric disorder, or other conditions that could interfere with subject's safety\*, obtaining informed consent or compliance to study procedures in the opinion of the investigator or GSK medical monitor.
- d. History of breast cancer or clinical breast examination finding suggestive of malignancy.
- e. History of malignancy within the past five years, except for basal cell carcinoma of the skin. Subjects with a priori malignancy who have had no evidence of disease for at least the past 5 years are eligible.
  - \*Investigator may consult with GSK Medical Monitor if condition could interfere with subject's safety
    - 10. Current or Previous Use of the following medications:

- a. Use of any 5-alpha-reductase inhibitor (e.g. Proscar, Propecia), any drugs with antiandrogenic properties (e.g. spironolactone, flutamide, bicalutamide, cimetidine, ketoconazole, progestational agents), or other drugs noted for gynaecomastia effects, or that could affect prostate volume, within the 6 months preceding the historical TRUS or Screening Visit and throughout the study (other than as study medication). Previous use of AVODARTTM should not be within 6 months of the baseline or historical TRUS.
- b. Anabolic steroids (subject must discontinue for 6 months prior to study entry to be eligible) and agree not to take them for the duration of the study.
- c. Phytotherapy for BPH within 2 weeks of Screening Visit and/or predicted to need phytotherapy during the study.
- d. Use of any alpha-adrenoreceptor blockers within 2 weeks of Screening Visit (i.e. indoramin, prazosin, terazosin, tamsulosin, alfuzosin, doxazosin, silodosin) and/or predicted to need any alpha blockers other than the study prescribed tamsulosin.
- e. Use of any alpha-adrenoreceptor agonists (e.g. pseudoephedrine, phenylephedrine, ephedrine) or anticholinergics (e.g. oxybutynin,tolterodine, darifenacin, solifenacin,propantheline) or cholinergics (e.g. bethanecol chloride) within 48 hours prior to all uroflowmetry assessments.
- f. Use of selective beta 3-adrenoceptor agonist (mirabegron) within 2 weeks prior to all uroflowmetry assessments.
- 11. Hypersensitivity to any alpha-/beta- adrenoreceptor blocker or 5-alpha-reductase inhibitor, or other chemically-related drugs.
- 12. Participation in any investigational or marketed drug trial within 30 days (or 5 half-lives of drug, whichever is the longer) preceding the Screening Visit and/or plans to participate in such a trial during the course of this study.

# 4.1.4. Other Eligibility Criteria Considerations

In order to assess any potential impact on subject eligibility with regard to safety, the Investigator must refer to the relevant document(s) for detailed information regarding warnings, precautions, contraindications, adverse events, drug interactions, and other significant data pertaining to the study drug(s) being used in this study. These documents include, but may not be limited to, the following: the dutasteride Clinical Investigator's Brochure (CIB) or equivalent document provided by GlaxoSmithKline (GSK), the dutasteride (AVODART) local product monograph, where available, the approved product label(s) for tamsulosin (Harnal D, Flomax) and dutasteride (AVODART), if applicable. Study Procedures Manuals will outline information contained in the local product monographs that must be relayed to patients (e.g. use of a condom to avoids exposure of his partner when taking the study drugs), as applicable to a specific country.

#### 4.1.4.1. Precautions

Investigator must refer to the relevant document(s) for detailed information regarding precautions as mentioned above. Local product monograph should be checked carefully to adhere to local labelling guidelines.

# 4.2. Permanent Discontinuation from Study Treatment and Subject Completion Criteria

# 4.2.1. Permanent Discontinuation from Study Treatment

Subjects will receive study treatment until completion of 2 years of study. In addition, study treatment may be permanently discontinued for any of the following reasons:

- deviation(s) from the protocol
- adverse event
- request of the subject
- subject who has BPH-related prostatic surgery or any minimally-invasive/nonsurgical intervention for treatment of BPH symptoms at any time during the study period
- investigator's discretion
- subject is lost to follow-up
- study is closed or terminated.

A subject, who experiences an AUR, does not need to be withdrawn from the study treatment. Any subject who has BPH-related prostatic surgery or any minimally-invasive/non-surgical intervention for treatment of BPH symptoms at any time during the study period must be withdrawn from the study treatment.

The primary reason for permanent discontinuation of study treatment must be documented in the subject's medical records and eCRF.

Once a subject has permanently discontinued from study treatment, the subject will not be allowed to be retreated or replaced.

All subjects who prematurely discontinue from study treatment may not necessarily be withdrawn from the study as further study procedures or follow-up may be performed (Section 6.3).

Subjects with sexual function related adverse events (contact GSK Medical Monitor if in doubt) leading to study withdrawal, will be followed up for up to 6 months after the last dose of study drug. The sexual function Targeted Follow-Up Questionnaire to be used for these subjects follow-up can be found in the Study Procedures Manual.

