Study ARI40005 considered the results from previous studies that explored the benefits of the combination of a single type 2 5ARI, finasteride, with different alpha blockers in BPH symptoms and outcomes in an average BPH population. The inclusion criteria for ARI40005 were designed to select men at increased risk for BPH progression, and included a requirement for baseline PV ≥30 mL, serum PSA levels ≥1.5 ng/mL, and an International Prostate Symptom Score [IPSS] ≥12 points. Efficacy measures included the combined endpoint of time to acute urinary retention (AUR) or BPH-related surgery after 4 years of treatment and symptom improvement after 2 and 4 years of treatment. Results of a planned Year 2 analysis demonstrated the efficacy and safety of co-administration, [Roehrborn, 2008]. Results of the planned Year 4 analyses for CombAT were published [Roehrborn, 2010]. The study demonstrated that in men with moderate to severe lower urinary tract symptoms (LUTS) and prostate enlargement (30 cc or greater), combination therapy with dutasteride (0.5mg) and tamsulosin (0.4mg) once daily provided a significantly greater degree of symptomatic benefit than either tamsulosin (0.4mg) or

dutasteride (0.5mg) monotherapy at the end of 2 and 4 years of treatment. In addition, at 4 years, dutasteride and tamsulosin in combination significantly reduced the risk of AUR and BPH related surgery compared to tamsulosin monotherapy. The data from the 4 year treatment study supports the long term use of dutasteride 0.5mg and tamsulosin 0.4mg co-administered in men with moderate to severe lower urinary track symptoms due to BPH and prostate enlargement.

In the overall CombAT population [4844 subjects], the observed safety and tolerability profile of combination therapy was generally consistent with the known safety profiles for the individual monotherapies. There was an observed imbalance in cardiac failure events [14 subjects (0.9%) in the combination group, 4 subjects (0.2 %) in the dutasteride group, and 10 subjects (0.6%) in the tamsulosin monotherapy group]. There was a higher incidence of ejaculation disorders [172 subjects (10.7 %) in the combination group compared to the individual monotherapies, 40 subjects (2.5%) in the dutasteride monotherapy group and 59 subjects (3.7%) in the tamsulosin monotherapy group]. No cardiac failure events were reported in the Asian subpopulation (a total of 325 subjects or 7% of the total population enrolled in the study).

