# 6.3. Treatment after Discontinuation of Study treatment or Discontinuation of Study

Post study treatment will not be provided as part of the protocol. Upon discontinuation from assigned study treatment, subjects may receive additional (non protocol) therapy at the discretion of the treating physician. The investigator is responsible for ensuring that consideration has been given to the post-study care of the patient's medical condition whether or not GSK is providing specific post-study treatment.

If a subject discontinues study treatment permanently after Visit 2 (post-randomisation) for any reason, other than lost to follow-up, the investigator should make every effort to complete the following activities listed below: (Note: the subject has the right to refuse any further contact for study-related follow-up information).

- End of Study Treatment Assessments as outlined in Section 7.2.2.5.
- Biannual follow-up for clinical events via telephone contact every 6 months relative to baseline visit (Visit 2) until the 2 year anniversary of randomisation. Any occurrence of death, AUR, BPH-related prostatic surgery or minimally-invasive/non-surgical intervention for BPH, prostate cancer /biopsy reported after premature withdrawal of study treatment, and outcomes of sexually related adverse events reported during the treatment period, should be fully documented in the eCRF and source documents. The purpose of the collection of these data is to more fully document study endpoints and related events.

No additional study activities other than those that are stated above are planned after a subject's permanent discontinuation from study treatment

A subject is considered a 'withdrawal' from the study when no study procedure has occurred, no follow-up has been performed and no further information has been collected for this subject from the date of withdrawal/last contact.

The primary reason for permanent discontinuation of study must be documented in the subject's medical records and eCRF.

Subjects who are withdrawn from the study after randomisation will not be replaced.

In the event that a subject is prematurely discontinued from the study treatment or withdraw from the study at any time due to an AE (as defined in Section 7.4.1, "Definition of an AE") or SAE (as defined in Section 7.4.2, "Definition of an SAE"), the procedures described in Section 7.4.7 ("AEs and SAEs") must be followed.

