**Updated Text: (additional text).** 

The pharmacokinetics of dutasteride and tamsulosin in Western subjects is well understood (CIB). In contrast, pharmacokinetic data for these two drugs in Chinese subjects are limited. Following a request to provide this information from the Regulatory Authority in China, subjects of Chinese origin living in China will participate in a PPK sub-study in this study, which aims to characterize the PK of dutasteride when dosed in combination with tamsulosin to Chinese men with BPH.

**Section:** 4.1.2 Inclusion Criteria.

**Action:** Additional inclusion criteria, applicable only to countries where the local product monograph for dutasteride mandates condom use for men with a female partner of childbearing potential to clarify the need for condom useage in men with female partners of childbearing potential.

**Rationale:** Some countries recommend the use of condoms in local dutasteride labels. The addition of this inclusion criteria makes study selection criteria consistent with these local labels.

**Original Text:** Not applicable.

**Updated Text**: Added: 9. Men with a female partner of childbearing potential must agree to use a condom up to 6 months after the last dose (applies only to countries where the local product monograph for dutasteride mandates condom use for men with a female partner of childbearing potential).

**Section:** 4.1.3 Exclusion Criteria.

**Action:** Additional exclusion criteria, to clarify that use of PDE-5 inhibitors are prohibited in the study.

**Rationale:** PDE-5 inhibitors are prohibited in the study.

Original Text: Not applicable.

**Updated Text**: Added: 10 f. Phosphodiesterase-5 (PDE-5) inhibitors for Erectile Dysfunction.

**Section:** 4.2.1 Permanent Discontinuation from Study Treatment.

**Action:** Additional text on actions to be taken for follow up of subjects discontinuing treatment because of a sexual function related AEs.

**Rationale:** sexual function related AEs are of particular interest in the indiction of BPH and the protocol amendment aims to clarify that subjects discontinuing treatment because of a sexual function related AEs must be followed up.

**Original Text:** Not applicable.

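### Section 4.2.1 ties the targeted sexual-function follow-up to study withdrawal, a state that Section 6.3 defines by the absence of follow-up, so read literally it misses men who stop treatment and stay in the study

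*Protocol*

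**What the plan says.** Protocol Section 4.2.1 first separates stopping treatment from leaving the study: "All subjects who prematurely discontinue from study treatment may not necessarily be withdrawn from the study as further study procedures or follow-up may be performed". Its next paragraph says that men with sexual function adverse events "leading to study withdrawal, will be followed up for up to 6 months after the last dose of study drug", and names the instrument: "The sexual function Targeted Follow-Up Questionnaire to be used for these subjects follow-up can be found in the Study Procedures Manual".

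Section 6.3 covers every man who permanently stops treatment after Visit 2, unless he is lost to follow-up. It asks for the end-of-treatment assessments of Section 7.2.2.5 and for follow-up "via telephone contact every 6 months relative to baseline visit (Visit 2) until the 2 year anniversary of randomisation". Outcomes of sexual adverse events that arose on treatment are among the items to be documented there. It then rules out any activity beyond that list and defines leaving the study: "A subject is considered a 'withdrawal' from the study when no study procedure has occurred, no follow-up has been performed". It ends by sending any man who stops treatment or leaves the study because of an adverse event to Section 7.4.7. That section has ongoing events monitored after treatment stops until they resolve or stabilise, or the man is lost to follow-up.

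Appendix 8 gives the Amendment 2 rationale for the Section 4.2.1 text: "subjects discontinuing treatment because of a sexual function related AEs must be followed up".

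**The concern.** The trigger in Section 4.2.1 and the definition in Section 6.3 do not fit together. The rule asks for up to six months of contact with men in a status that is recognised by the absence of contact. The man most likely to provide the information stops treatment because of the event but still takes calls. He is not a withdrawal, so the literal rule passes him over.

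Tolerability against tamsulosin alone is a stated objective (Section 2.2.2). Section 1.1 reports ejaculation disorders in "172 subjects (10.7 %) in the combination group compared to the individual monotherapies", with 3.7% on tamsulosin alone. If one site gives the questionnaire to everyone who stops for a sexual event and another gives it only to men who leave the study, the questionnaire data will come from a set that depends on how each site read the rule. A comparison between arms on such a set would be hard to interpret.

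**Working it through.** No stated sample size, power or alpha is in dispute. The check sets the sections side by side and then examines the timing.

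**1. Trigger.** Take two men who each have a sexual adverse event.

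- Man A stops treatment because of it and stays in follow-up. Section 6.3 gives him the end-of-treatment visit and the calls, and Section 7.4.7 applies while the event continues. He has not left the study, so Section 4.2.1 does not assign him the questionnaire.
- Man B leaves the study because of it. Section 4.2.1 assigns him the questionnaire, but under Section 6.3 he counts as a withdrawal because "no follow-up has been performed and no further information has been collected for this subject from the date of withdrawal/last contact".

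The rule therefore misses A, who can be reached, and selects B, who by definition is not being reached.

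**2. Instrument.** The closed list in Section 6.3 contains the end-of-treatment assessments and the calls. The assessments in Section 7.2.2.5 include the PAS-SFI, given when treatment stops, but not the targeted questionnaire. No contact is timed from the last dose.

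**3. Timing, if the calls are the vehicle.** Section 4.2.1 does not say that they are, so this step is conditional. Calls every 6 months from baseline to the second anniversary fall at Months 6, 12, 18 and 24. Let the last dose be at month t, with 0 < t < 24, so the window is (t, t + 6].

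- Calls inside the window: exactly one for every t.
- The window ends by Month 24 when t + 6 ≤ 24, that is, t ≤ 18.
- For t > 18 it overruns Month 24 by t − 18 months, between 0 and 6. For a last dose at Month 22, the only call comes 24 − 22 = 2 months later, and 22 − 18 = 4 months of the window lie beyond the schedule.

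**4. Size of the timing part.** The protocol gives no distribution of stopping times. If they were uniform over 24 months:

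- Share stopping after Month 18: (24 − 18)/24 = 25%.
- Mean overrun in that group: 6/2 = 3 months.
- Share of all window time inside Month 24: 1 − 0.25 × 3/6 = 87.5%.

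Section 9.2.1 assumes 20% discontinuation for all reasons: 0.20 × 586 = 117 men. After Month 18 that gives 0.25 × 117.2 = 29 men, or 12 to 47 if the late share is 10% to 40%. These counts cover stopping for any reason. Men who stop for a sexual event are an unknown part of them, so within each assumed share the count is a ceiling.

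**The case against.** The strongest reply is that these men are followed anyway. Section 6.3 asks for sexual adverse event outcomes from every treatment discontinuer not lost to follow-up, with no study-withdrawal condition. It also sends men who stop because of an adverse event to Section 7.4.7, which has no Month 24 stop. This stands, and it limits the point to the targeted questionnaire and a uniform window.

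Two further replies also stand. The six months in Section 4.2.1 is a maximum, so a single contact at two months does not breach it. The timing and mode of the questionnaire may be set in the Study Procedures Manual, which is not available here; that is why the Month 24 limit is stated only conditionally.

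A fourth reply is that the Section 6.3 definition looks backwards. It classifies a man from his last contact and does not forbid contact before then. That is a fair reading of its purpose, but it does not rescue the trigger. A status established only once contact has ceased cannot tell a site when to begin contact.

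Finally, the wording might be a loose synonym for stopping treatment. The sentence just before the rule separates the two states, and Section 6.3 does so again, so a site has no reason to read them as the same. The amendment rationale shows what was probably meant, but it is only context: the contradiction rests on Sections 4.2.1 and 6.3 alone.

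**Conclusion.** The point holds as an internal contradiction in a safety-data rule. The trigger in Section 4.2.1 does not fit the definition in Section 6.3, and the closed list in Section 6.3 leaves out the instrument that Section 4.2.1 relies on. This part needs no assumption beyond reading the two sections literally.

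The timing part is smaller. It applies only to last doses after Month 18 and only if the calls carry the follow-up. The 25% share also assumes uniform stopping times.

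Three stronger readings are tempting and are not supported:

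- A reader might infer that almost no one will be followed for sexual events. That confuses the literal reach of one rule with the follow-up that Sections 6.3 and 7.4.7 provide.
- A reader might apply the ejaculation-disorder percentages in Section 1.1 to this trial's arms to count the men affected. Those percentages are for men with any such event in a four-year trial using tamsulosin 0.4 mg. The protocol gives no rate of stopping because of one.
- A reader might infer that the follow-up was added to show whether these effects reverse. Appendix 8 says only that the events are of particular interest and that the men must be followed.

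The primary analysis is unaffected. The contradiction should be corrected because the rule cannot operate as written and the correction is cheap.

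**What to change.** Reconcile Sections 4.2.1, 6.3 and 7.4.7 so that they give one trigger, one instrument and one end date.

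- In Section 4.2.1, word the trigger as permanent discontinuation of study treatment because of a sexual function adverse event. This agrees with the population of Section 6.3 and with the Amendment 2 rationale.
- Add the targeted questionnaire to the activities listed in Section 6.3, and say whether it is completed at the existing calls or at a contact timed from the last dose.
- State whether collection continues past Month 24 for men whose last dose falls after Month 18, and how that end date relates to the open-ended monitoring in Section 7.4.7.

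This concerns data collection only. It changes no treatment and no rule for stopping treatment.

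The cost is a wording amendment and possibly one extra contact for a few late discontinuers, whose data would arrive after their Month 24 date. The questionnaire already exists in the Study Procedures Manual. Section 7.4.5.1 already collects partner pregnancies until six months after the last dose, so collection beyond Month 24 is not new to this protocol.
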